## **8.3 Statistical methods**

### **Primary Objectives**

The outcome measure for primary endpoint will be the pharmacokinetics of posaconazole, measured as the area under the curve of the concentration vs time gradient over the first 24 hours (AUC0-24). We will be measuring the concentration of posaconazole (AUC-Drug) in brain interstitium using the MDC. The AUC-Drug will be estimated by the trapezoid rule, based on the number of timepoints available for the particular evaluable patient. Brain posaconazole concentration at steady-state will also be summarized using descriptive statistics. The AUC-Drug will be estimated by standard noncompartmental or compartmental analysis as performed by Phoenix® WinNonlin version 6.3 (Pharsight Corporation, Mountain View, CA, USA).

The PK variables will be tabulated and descriptive statistics calculated. The AUCs will be summarized by mean and standard deviation or median and range if there is large variation from patient to patient. Means and standard deviation or mean and range will be presented for Cmax and AUC.

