### 1.2 Primary Study Endpoints

Establish the neuro-pharmacokinetic profile of posaconazole, using microdialysis catheters (MDC). This will be based on the assessment of the concentration versus time curves of drug in the dialysate fluid, collected over a 24-hour period after surgery.

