## 2.3

### Study Rationale

Both ketoconazole and posaconazole are FDA-approved anti-fungal agents with a well-established side effect and safety profile. Ketoconazole and posaconazole have shown efficacy in reducing tumor cell proliferation in our *in vitro* studies. Furthermore, both have also shown efficacy, mediated at least in part through inhibition of HK2 activity, in our animal models with dosing concentration and schedules that are documented as safe in humans.[58] As a drug, posaconazole has a more predictable half-life than ketoconazole and has less off-target effects. Therefore, the proposed trial will focus on the role of posaconazole exclusively. As a first step, demonstration of adequate penetrance of study drug in brain and tumor tissue (pharmacokinetics) and biological effect (inhibition of glycolysis and subsequent tumor cell death) is necessary prior to large scale clinical studies. A total of 5 control participants will be included in this study as we specifically want to assess for pharmacodynamic differences too. The

addition of a control group to this study rather to both the studies (ketoconazole study is a separate protocol) is because we feel posaconazole may be a more promising drug for moving forward.

Plasma drug concentration measurements are an unreliable method to assess delivery of drugs across the blood-brain barrier. In contrast, intracerebral MDC monitoring allows for approximate measurements within extracellular fluid (ECF) sampling of the brain. MDC placement within the brain is not a novel technique and has been utilized routinely in the ICU setting to measure brain metabolism by sampling of ECF of traumatic brain injury patients [59-61].

MDC are now FDA-approved and are being placed routinely with intracranial pressure monitors. This method allows for continuous measurement of ECF within a tumor or normal tissue. The dialysis probe has a semipermeable membrane which is less than 1 mm in diameter into which two sections of microcatheter are fused. Previous studies have demonstrated the feasibility of keeping the catheters in place of critically injured patients for up to 2 weeks [62-64].

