When placed at the time of surgical resection, the microcatheters are stereotactically implanted, placing the probe within the desired brain and/or tumor region. Externally, the catheter is connected to a syringe pump, which delivers a low flow rate ( $\mu\text{l}/\text{min}$ ) of continuous perfusion fluid (Lactated Ringers or artificial CSF) and dialysate is collected in a microvial from the outlet tube. This sterile, single use catheter is minimally invasive and developed to achieve optimal diffusing characteristics similar to passive diffusion of a capillary blood vessel. Just as in the function of brain capillary vessel, water, inorganic ions and small organic molecules freely diffuse across the membrane of the probe, whereas proteins and protein bound compounds are impermeable. Additionally, lipophilic compounds are poorly recovered. Therefore, assessment of pharmacokinetics of drug using MDC provides valuable insight relevant to its anti-neoplastic properties.

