#### **Microdialysis collection/monitoring**

After the imaging confirms proper placement of the MDC tip, the inlet tubing will be connected to a portable syringe pump to perfuse artificial CSF (Perfusion Fluid CNS, ref. no. P000151, CMA, Solna, Sweden) at a rate of 1.0  $\mu$ l/min. The inlet tubing of the catheter will be connected to a CMA 107 Microdialysis Pump (ref. no. P000127, CMA, Solna Sweden). A microvial will be connected at the end of the outlet tubing to collect perfusate.

Concurrently, a plastic microvial (Ref. No. P000001, CMA, Solna, Sweden) will be placed in the vial holder at the end of the outlet tubing to collect dialysate. This microvial can hold up to 200 $\mu$ L of fluid. It will need to be replaced with a new one every 3 hours. During daytime work week hours, trained research coordinators, in coordination with nursing team will collect dialysate and replace the microvials. At all other times, these tasks will be performed by the study PI, [name].

Dialysate sample collection will begin in the morning of postoperative day 1. If the participant was able to tolerate the AM dose of study drug (study drug group only), sample collection will begin immediately after drug administration. Otherwise, sample collection will begin within the same allotted time period (i.e. 8AM +/- 4 hours). For the control group, sample collection will be at 8 AM +/- 4 hours. The initial sample will be labeled as the 'Time 0' sample. Additional samples will be collected at 15 and 30 minutes, along with 1, 2, 4, 6, 8, and 24 hours after 'Time 0'.

Microvials containing the dialysate should be stored in an ultralow temperature freezer ( $\leq 70^{\circ}\text{C}$ ) until they can be batch analyzed by LC/MS/MS.

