### **11.2 Potential Benefits to Others**

The use of posaconazole as a drug against HGGs has never been formally studied and this is a unique opportunity to study this possible indication. If posaconazole successfully demonstrates effective accumulation in brain and tumor interstitium and result in the expected pharmacodynamics changes, it could be of major importance in improving the outcome of patients with HGGs.

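### Section 8.3 reports dialysate AUC, Cmax and steady-state values as posaconazole concentration in brain interstitium, with no recovery determination or correction specified

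*Combined protocol and SAP*

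**What the plan says.** Section 1.2 bases the primary endpoint on the "concentration versus time curves of drug in the dialysate fluid", collected over 24 hours after surgery. Section 8.3 (Primary Objectives) takes AUC0-24 as the outcome measure and describes it differently: "We will be measuring the concentration of posaconazole (AUC-Drug) in brain interstitium using the MDC". The same section adds a descriptive summary of the steady-state brain concentration, and summaries of Cmax and AUC. On estimation it says: "The AUC-Drug will be estimated by the trapezoid rule, based on the number of timepoints available for the particular evaluable patient". It also names a noncompartmental or compartmental analysis in a software package. Neither route contains a recovery term.

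Section 2.3 sets out what the catheter can measure. It says "intracerebral MDC monitoring allows for approximate measurements within extracellular fluid (ECF) sampling of the brain". Of the membrane it says that small molecules diffuse freely, "whereas proteins and protein bound compounds are impermeable", and then: "Additionally, lipophilic compounds are poorly recovered".

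The Microdialysis collection/monitoring text in 7.2.5 fixes the pump, the perfusate and flow ("Perfusion Fluid CNS, ref. no. P000151, CMA, Solna, Sweden) at a rate of 1.0" µl/min), the nine sampling times and the mass spectrometry assay. The Intra-operative procedure text in 7.2.3 fixes the catheter type and its 10 mm membrane. Neither describes a step to determine recovery.

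**The concern.** The two sections name different quantities for one endpoint. What leaves the catheter is dialysate. What 8.3 says will be reported is the concentration in the fluid around the cells. The two agree only if recovery across the membrane is complete, and 2.3 gives reasons not to assume that.

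The label affects interpretation. Section 8.2 describes the trial as an assessment of whether posaconazole penetrates brain tissue sufficiently, and treats a negative result as informative for ending development early. Section 11.2 looks ahead to the case in which the drug "successfully demonstrates effective accumulation in brain and tumor interstitium". A low or undetectable dialysate AUC could arise because little drug reached the interstitium or because little of it crossed the membrane. The dialysate data alone cannot separate the two. A report that followed 8.3 literally would present the low value as a low brain concentration.

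The problem is sharpest at the non-enhancing boundary. Under 7.2.3, a patient whose enhancing tumor is completely resected receives one catheter, in the non-enhancing margin within 5 mm of the cavity. The tissue samples come from the center of the tumor and from its capsule. No tissue sample is planned from the margin, so dialysate is the only drug measurement there.

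**Working it through.** The plan states no recovery figure, effect size or precision target for this endpoint, so there is no figure to reproduce. The check concerns scale.

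**Inputs from the documents**
- Sampling times: 0, 0.25, 0.5, 1, 2, 4, 6, 8 and 24 hours (7.2.5).
- Estimator: trapezoid rule (8.3).
- Only unbound drug crosses the membrane (2.3).
- Molecular weight of posaconazole: 700.8 (7.4.1).

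**Assumption.** Relative recovery R, the ratio of dialysate to unbound interstitial concentration, is not given and is shown as a range.

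**Step 1: concentration.** C(dialysate) = R × C(unbound interstitial).

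**Step 2: AUC.** The trapezoid rule is linear in the concentrations. With constant R, AUC(dialysate) = R × AUC(unbound interstitial), so the understatement factor is 1/R. This was confirmed on the nine planned times with two illustrative interstitial profiles in arbitrary units. A flat profile has AUC 24.0, and at R = 0.10 the dialysate AUC is 2.4. A peaked profile has AUC 28.842, and at R = 0.10 the dialysate AUC is 2.884. The factor is 10 in both. Cmax and the steady-state value scale in the same way.

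**Step 3: size over assumed recoveries**

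| Assumed R | Factor 1/R | Unbound 5 µM would read |
|---|---|---|
| 0.90 | 1.11 | 4.5 µM |
| 0.50 | 2 | 2.5 µM |
| 0.20 | 5 | 1.0 µM |
| 0.10 | 10 | 0.5 µM |
| 0.05 | 20 | 0.25 µM |

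The 5 µM column only illustrates scale. The plan does not apply that threshold to dialysate.

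**Step 4: spread.** If R varies between catheters independently of the true AUC, the coefficient of variation (CV) of the reported AUC is √[(1 + CV_AUC²)(1 + CV_R²) − 1]. With an assumed true CV of 30% and a recovery CV of 40%, this is √(1.09 × 1.16 − 1) = √0.2644 = 0.514. The reported CV would be about 51% instead of 30%, in five treated patients. Both inputs are assumptions.

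**The case against.** The strongest reply is that the trial does not use dialysate posaconazole to decide anything. The drug criterion in 8.2 is at least 5 µM in resected tumor in at least 2 of 5 patients. The other two success metrics concern lactate and pyruvate. The primary endpoint is descriptive, in a Phase 0 pilot with five treated patients and no hypothesis test. Section 1.2 already names the dialysate matrix, and 2.3 openly states the limits of the method. All of this stands, and it lowers the severity. It does not remove the mismatch, because 8.3 governs what is reported and does not carry the limits of 2.3 forward.

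Three stronger readings are tempting, and the documents do not support them:

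- **That posaconazole is known to be poorly recovered because it is lipophilic.** Section 2.3 makes a statement about lipophilic compounds in general. Nothing says that posaconazole is one; 7.4.1 gives its class, structure and molecular weight. The point does not need this link. Section 2.3 excludes bound drug and calls the measurement approximate, and nothing in the documents supports complete recovery.
- **That the go/no-go drug criterion is biased.** It uses resected tumor, not dialysate, so it is not directly affected.
- **That a planned comparison of dialysate with plasma or tissue is invalid.** The only ratio planned is tumor to blood (7.2.3). No dialysate ratio is specified.

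It can also be said that the absence of a correction is inferred from silence. That is fair. The supportable statement is that none is specified.

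**Conclusion.** The point holds as a labelling and interpretation defect in the declared primary endpoint. It should be fixed, but it does not undermine the design. Followed as written, 8.3 would report dialysate AUC0-24, Cmax and steady-state values as brain interstitial concentrations, which are biased low whenever recovery is below 100%.

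The factor of 1/recovery applies to unbound interstitial exposure only. A reader might take it as the understatement of total brain exposure; it is not, because bound drug is outside what the catheter samples. The size cannot be narrowed from the documents. The factors of 2 to 20 rest on assumed recoveries of 50% to 5%, and on recovery that is constant over the 24 hours. Constant recovery would leave the shape of a patient's profile intact while still scaling its AUC and Cmax.

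Tissue concentration in the same patients helps to interpret a low dialysate value in sampled tumor. It cannot do so for the non-enhancing margin.

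**What to change.** 1. In 8.3, label AUC0-24, Cmax and the steady-state concentration as *dialysate, unbound, not corrected for recovery*, in line with 1.2, and remove the description of them as brain or interstitial concentrations.
2. In 8.3, state that a low or undetectable dialysate value is not by itself evidence of non-penetration, and that tissue concentration supports conclusions about the sampled tumor only.
3. Optionally, if in vitro recovery of posaconazole is available for the same catheter type, perfusate and 1.0 µl/min flow, report in-vitro-corrected values (raw value divided by recovery) beside the raw ones. State that in vitro recovery may differ from recovery in tissue. A single factor does not remove between-catheter variation and cannot rescue an undetectable value.

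Items 1 and 2 are wording only and add no patient burden. Their price is a more cautious primary claim. Item 3 needs bench work if the recovery figure does not already exist, and the correction of 8.3 does not depend on it.

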### **Study Population**

Only patients who are eligible and take posaconazole according to protocol specifications (study drug arm only) **and** have undergone successful MDC implantation will be considered evaluable and included in the study analysis. Otherwise, enrolled patients will be replaced. All eligible patients for whom analyzable dialysate samples were obtained for at least 7 of the 9 time points will be considered evaluable for the primary study endpoint. Patients who are not evaluable will be replaced.

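### A patient without the 24 h dialysate sample still counts as evaluable for AUC0-24, and the stated trapezoid rule would then stop at 8 h or 6 h

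*Combined protocol and SAP*

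**What the plan says.** Section 8.3 (Primary Objectives) defines the primary outcome as the area under the dialysate concentration-time curve over 24 hours, AUC0-24. The area is to be "estimated by the trapezoid rule, based on the number of timepoints available for the particular evaluable patient". Two sentences later the same area is to be "estimated by standard noncompartmental or compartmental analysis" in WinNonlin. The AUCs are then summarised across patients by mean and SD, or by median and range if variation is large. The section's last sentence names a mean for AUC with either SD or range.

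Section 7.2.5 (Microdialysis collection/monitoring) sets the sampling times, counted from a first sample labelled Time 0. For the later ones it says: "Additional samples will be collected at 15 and 30 minutes, along with 1, 2, 4, 6, 8, and 24 hours after" that first sample. On the collecting microvial it adds: "It will need to be replaced with a new one every 3 hours".

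Section 8.2 (Study Population) sets the evaluability rule. For eligible patients it reads, in part: "analyzable dialysate samples were obtained for at least 7 of the 9 time points will be considered evaluable for the primary study endpoint". It names no sample as mandatory, and continues: "Patients who are not evaluable will be replaced".

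**The concern.** The evaluability rule treats the nine samples as interchangeable, and for a 24-hour area they are not. Eight of them fall in the first 8 hours. The remaining 16 hours rest on one sample. A patient who lacks it passes the 7-of-9 rule and so is not replaced. On the available timepoints, that patient's trapezoid has nothing to integrate after 8 h.

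Under the stated trapezoid rule, an area over a third or less of the interval would be averaged with full 24-hour areas under one label. With five treated patients, one such value is enough to move the summary of the primary outcome. The plan has no rule for this case: no extrapolation, no separate label and no exclusion.

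**Working it through.** **Inputs from the documents.** Sampling times 0, 0.25, 0.5, 1, 2, 4, 6, 8 and 24 h (7.2.5). At least 7 of 9 samples (8.2). Linear trapezoid on the available points (8.3). Five evaluable patients on drug (7.1). Plasma Tmax 4-5 h and half-life 15-35 h (7.4.1); mean half-life 26-31 h (7.2.1 and 7.4.2).

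**Assumed.** A flat profile needs no kinetic input. The second profile is one-compartment with first-order absorption, at steady state with a 24 h dosing interval, and applies the plasma Tmax and half-life to dialysate.

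**Step 1: the plan's own count.** Time 0 plus eight later times gives 9, as section 8.2 states.

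**Step 2: permitted sample sets.**
- With 9, 8 or 7 samples: 1 + 9 + 36 = 46 sets.
- Without 24 h: 1 (only 24 h missing) + 8 (24 h and one other missing) = 9 sets.
- Of these 9, the last sample is at 8 h in 8 sets and at 6 h in 1 set (8 h and 24 h both missing).
- With 24 h: 46 - 9 = 37 sets.

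These count patterns. They are not probabilities.

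**Step 3: share of AUC0-24 that the trapezoid returns.** For a flat profile with Time 0 present, the share is (last sample time)/24: 8/24 = 33% and 6/24 = 25%. If Time 0 is also missing, it is (8 - 0.25)/24 = 32%.

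For the assumed profile, trapezoid divided by true AUC0-24:

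| Sample set | Half-life 26-31 h | Half-life 15-35 h |
|---|---|---|
| All 9 samples | 1.001-1.006 | 1.001-1.020 |
| Any permitted set with 24 h | 0.980-1.007 | 0.977-1.025 |
| Last sample at 8 h (8 sets) | 0.354-0.378 | 0.350-0.412 |
| Last sample at 6 h (1 set) | 0.268-0.282 | 0.266-0.305 |

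The lowest values in the 8 h row come from the set that also lacks Time 0. The 7-of-9 tolerance therefore costs almost nothing as long as the 24 h sample is kept.

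**Step 4: effect on the mean of five.** If one of five patients with otherwise equal areas has ratio r, the mean falls by (1 - r)/5.
- Flat, ending at 8 h: (1 - 0.333)/5 = 13.3%. Ending at 6 h: (1 - 0.25)/5 = 15.0%.
- Assumed profile, half-life 15-35 h, ending at 8 h: (1 - 0.412)/5 = 11.8% to (1 - 0.350)/5 = 13.0%. Ending at 6 h: (1 - 0.305)/5 = 13.9% to (1 - 0.266)/5 = 14.7%.

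Overall this is about 12-15%. In the flat case, four values of 1 and one of 1/3 also create a CV of 34% where there is no true variation.

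**Step 5: what the choice of method is worth.** A method that carries a flat curve from 8 h to 24 h gives 24/8 = 3 times the truncated value for the same patient.

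**Step 6: frequency, illustration only.** Suppose each sample is lost independently with probability 2%, 5% or 10%. The chance that an evaluable patient lacks 24 h is then 2.0%, 4.8% or 8.6%. The chance that at least one of five does, 1 - (1 - x)^5, is 10%, 22% or 36%. The documents support none of these loss rates.

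**The case against.** The strongest objection is that the plan does not commit to the truncated value. Section 8.3 also allows noncompartmental or compartmental analysis, and a compartmental fit can give an area to 24 h without a 24 h sample. This stands in part. A reader might infer that a truncated area is certain to enter the AUC0-24 summary, and the documents do not support that. They contain one sentence that would produce it and another that might avoid it, with neither named as primary.

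A reader might also take 9 of 46 patterns to mean that about a fifth of patients would be affected. That does not follow. The 24 h sample is a planned Visit 6 activity, the catheter is removed only after collection ends, and no loss rate is given.

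Third, the 3-hourly vial changes mean that dialysate from 8-24 h should physically exist. That is fair, but the plan does not name those vials as time points, so they count neither towards the nine nor in the area.

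Fourth, the consequence is limited. The summary is descriptive, with no test or threshold on AUC. The success metrics in section 8.2 rest on tumour drug concentration, lactate and pyruvate. Anyone who infers that the decision to proceed is at risk goes beyond the documents. The plan also says "The PK variables will be tabulated and descriptive statistics calculated", so a low value could be noticed, and a median would be less sensitive to it. Neither corrects the value.

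Finally, the kinetic ratios borrow plasma values, while section 2.3 warns that protein-bound compounds do not cross the membrane and lipophilic ones are poorly recovered. Only the flat-profile figures avoid that borrowing.

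**Conclusion.** The point holds as a gap in the rules for the primary outcome, and should be fixed. The evaluability rule admits a patient without the 24 h sample, and the stated trapezoid rule then returns 33% or 25% of AUC0-24 for a flat profile. The assumed steady-state profile gives 35-41% or 27-31%. One such patient in five lowers the mean by about 12-15%, provided the areas are otherwise similar and the trapezoid is the method used. The counts and flat-profile ratios follow directly from the schedule; the other ratios depend on plasma kinetics being applied to dialysate. How often it would occur is unknown. Only the descriptive primary PK estimate is affected.

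**What to change.** In section 8.3, name one primary AUC method. Report any curve without a 24 h sample separately as AUC0-tlast, outside the AUC0-24 mean or median.

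In section 8.2, keep the 7-of-9 rule and add that the 24 h sample must be among them for a patient to enter the AUC0-24 summary. State also that a patient lacking only this sample stays in the study analysis and need not be replaced. The two changes belong together. If the 24 h sample were simply made a condition of evaluability, the existing replacement sentence would bring in another patient, dosed and given a catheter, for a descriptive summary.

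The cost is wording in two sections. The downside is that the AUC0-24 summary may rest on fewer than five patients, so the number contributing should be shown beside it.

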### 8.2 Sample size determination

#### Design

This is an exploratory (pilot) study to assess whether posaconazole can penetrate brain tissue at sufficient enough levels to result in expected downstream biological effects on glycolysis and tumor cell survival. Five evaluable patients will be studied for this trial. The sample size justification is not based on statistical rationale but clinical affordability.

The following metrics will be used to define success and support the decision to proceed with advanced phase trials:

- Detection of  $\geq 5\mu\text{M}$  concentration of either drug in resected tumor in at least 2 of 5 patients in each arm – a value that is within the range needed to achieve efficacy for CNS fungal infections and to achieve 50% glioma tumor cell kill *in vitro* based on our prior published report (ref 58); AND
- Reduction in average lactate and pyruvate concentrations in both resected tumor and dialysate fluid (using MDCs) in the treated cohorts compared to controls; AND
- Steady concentration of lactate and pyruvate over 24 hours of monitoring with MDCs in control participants.

The rationale for the above is based on the notion that any tumor penetration by drug, with concomitant effect on glycolysis, warrants further in-depth analysis as our therapeutic options for these deadly tumors are currently very limited. Intra-tumoral drug concentration on the lower range would still be promising and warrant dose-escalation studies, as the currently selected dosing is based on anti-fungal regimens that are known to be safe. Phase II studies for assessing tumor response would be warranted if substantial tumor penetration together with expected biological effect is observed. A negative trial would nonetheless have value as it would serve as an efficient means of determining whether or not either of ketoconazole or posaconazole hold promise against GBMs, as part of a “fail early” approach to drug-development, while minimizing the human and financial cost investment.

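### Section 8.3 gives the primary AUC two summary rules that disagree when patients vary widely, with an undefined switch made after seeing five values and no rule for a missing 24-hour sample

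*Combined protocol and SAP*

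**What the plan says.** Section 8.3, under Primary Objectives, makes the 24-hour AUC of posaconazole in brain interstitium the primary outcome measure. It contains two sentences on how to summarise it. The first lets the summary depend on the spread: "The AUCs will be summarized by mean and standard deviation or median and range if there is large variation from patient to patient". The second, which follows directly and also covers Cmax, keeps the mean whatever the spread turns out to be: "Means and standard deviation or mean and range will be presented for Cmax and AUC".

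It also contains two sentences on how to calculate it. One names a single method: "The AUC-Drug will be estimated by the trapezoid rule, based on the number of timepoints available for the particular evaluable patient". The other, a little further on, leaves a choice between two classes of method: "The AUC-Drug will be estimated by standard noncompartmental or compartmental analysis".

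Section 8.2 sets the size at five evaluable patients and gives the reason: "The sample size justification is not based on statistical rationale but clinical affordability". Section 8.2 (Study Population) counts a patient as evaluable for the primary endpoint with analyzable dialysate at any 7 of the 9 times. Section 7.2.5 sets those times at 0, 0.25, 0.5, 1, 2, 4, 6, 8 and 24 hours, with nothing between 8 and 24 hours.

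**The concern.** A primary endpoint should have one result that is fixed before the data are seen. Here the centre to be reported (mean or median) turns on an undefined judgement about spread, made with the five values in view, and a second sentence gives a different answer in the very case where the judgement matters. The plan also names a second class of estimator without saying which is primary, and does not say what AUC0-24 means for a patient with no sample after 8 hours. What is at stake is the brain exposure figure that the trial will report, and that later work would quote.

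**Working it through.** **1. The two summary sentences side by side.**

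| Spread between patients | First sentence | Second sentence | Agree? |
|---|---|---|---|
| Not large | mean, SD | mean, with SD or range | Yes, if SD is chosen |
| Large | median, range | mean, with SD or range | No |

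Neither sentence gives a threshold for large, and the second gives no rule for choosing SD or range.

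**2. How far apart mean and median can be in five values.** The plan states no AUC, SD or CV, so there is no figure to reproduce and the CV must be assumed. Take log-normal AUCs with log-scale SD s = sqrt(ln(1 + CV²)). At CV 50%, s = sqrt(ln 1.25) = 0.472. Simulating sets of five (1,000,000 per CV) and comparing the mean with the median of the same five values gives:

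| Assumed CV | Mean/median, 5th to 95th percentile | Differ by more than 20% |
|---|---|---|
| 20% | 0.93 to 1.13 | 1% |
| 30% | 0.90 to 1.22 | 6% |
| 50% | 0.88 to 1.46 | 25% |
| 80% | 0.86 to 1.99 | 45% |
| 100% | 0.85 to 2.44 | 54% |

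An invented illustration of the large-spread case: AUCs of 40, 60, 100, 200 and 600 have mean 1000/5 = 200 and median 100.

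**3. Choice of estimator with complete sampling.** The trapezoid rule is itself the usual noncompartmental method, so those two statements are compatible. Only the compartmental option is different. To size it, build a one-compartment steady-state profile with 24-hour dosing:

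C(t) ∝ ka/(ka − k) × [e^(−kt)/(1 − e^(−24k)) − e^(−ka·t)/(1 − e^(−24ka))], with k = ln 2 / half-life.

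Its exact AUC0-24 is 1/k in these units, which stands in for a correctly specified compartmental fit. The inputs are half-lives of 26-31 h (sections 7.2.1 and 7.4.2) and 15-35 h (section 7.4.1), with ka set either to give a single-dose Tmax of 4 or 5 h (section 7.4.1) or to 0.3 or 0.7 per hour (assumed). The dialysate is assumed to have the plasma profile shape.

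Example, half-life 26 h and Tmax 4 h: k = 0.693/26 = 0.02666, so AUC0-24 = 1/0.02666 = 37.5. The nine-point linear trapezoid gives 1.007 times this. Over all the inputs, the nine-point error runs from −0.5% to +2.2%.

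**4. The same profile without the 24-hour sample.** Eight of nine points remain, so the patient is still evaluable. The trapezoid stops at 8 h. In the example it gives 14.5, and 14.5/37.5 = 39%. Over all the inputs the range is 35% to 42%. A compartmental fit would instead extrapolate to 24 h.

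Of the 46 ways to have at least 7 of 9 points (36 + 9 + 1), 9 lack the 24-hour sample. With the Tmax-based inputs, the worst evaluable pattern gives 28-32%. Where the 0 h and 24 h samples are both kept, the error stays between −0.8% and +3.1%.

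**The case against.** - **The contradiction may be a typing slip.** Mean and range, one sentence after median and range, could well be meant as median and range. This is plausible, and it would remove the conflict. It would leave the undefined switch in place.
- **The effect depends on an assumed CV.** This stands. At CV 20-30% the choice hardly matters. It becomes material from about CV 50%, which the plan neither supports nor excludes. The sentences conflict only when spread is judged large, which is where the gap between mean and median tends to be widest.
- **Tabulation may already cover it.** Section 8.3 says the PK variables will be tabulated. If that means a per-patient listing, a reader could compute any summary. The wording does not say so, and it does not settle which figure is the primary result.
- **No decision depends on it.** A reader might infer that the success decision is exposed to a post hoc choice. It is not. The section 8.2 metrics use drug concentration in resected tumor and lactate and pyruvate levels, and section 8.3 plans no test of AUC.
- **The estimator conflict is small.** A reader might infer that trapezoid and noncompartmental are rival methods, or that the choice is material in general. Step 3 shows neither holds with complete sampling.
- **Negative exposure.** A reader might infer that mean and SD would imply negative exposure. That follows readily only for mean minus 2 SD, an interval the plan does not propose. Mean minus 1 SD falls below zero in about 0.4% of samples at CV 50% and 8% at CV 80%.

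**Conclusion.** The point holds as a reporting defect in the primary endpoint. As written, the two summary sentences conflict when spread is large, and the switch between summaries has no threshold and is applied after seeing five values. The size depends on an unknown CV: a mean-median gap above 20% occurs in about 1% of samples at CV 20%, rising to 54% at CV 100%, under log-normality at n = 5.

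The loose compartmental alternative is worth about 2% at most with nine samples. The larger exposure is a missing 24-hour sample, which the 7-of-9 rule permits. The trapezoid then yields about 35-42% of AUC0-24, assuming a one-compartment profile and a dialysate curve shaped like plasma. Misfit of a compartmental model was not examined.

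The documents do not support a claim that an error rate or go/no-go outcome changes.

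**What to change.** In section 8.3:

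- Delete the large-variation switch and the second summary sentence.
- Always list each patient's AUC0-24 and Cmax, and always report median with range. Add geometric mean with geometric CV when all values are quantifiable. That condition is needed because a geometric mean is undefined if any AUC is zero, and section 2.3 warns that lipophilic compounds are poorly recovered by the catheter and protein-bound ones do not cross its membrane.
- Name the noncompartmental trapezoid on actual sampling times as the primary estimator, with compartmental analysis supportive.
- Require the 24-hour sample for AUC0-24. Without it, report that patient's AUC to the last sample (AUC0-tlast) and do not pool it with AUC0-24. Naming the trapezoid as primary without this rule would fix the plan on the estimator that falls short in that case.

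The matching edit in section 8.2 is to say whether a patient without the 24-hour sample is replaced. The cost is wording only, with no new measurements. The one possible consequence is fewer than five AUC0-24 values, or a replacement patient, if a 24-hour sample is lost.
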